### 5.6.4 Change from baseline in Upper Limb Module Test at 15 months

The upper limb module test (Mazzone et al. 2011) referenced in the protocol was developed to assess the upper limb functional abilities in SMA patients using 9 items. However, a revised version of the upper limb module test developed by the Upper Limb Module Working Group will be performed in this study consisting of 20 items. The first item is assessed on a seven point scale ranging from 0 - 'No useful function' to 6 – 'Can abduct both arms simultaneously elbows in extension in a full circle until they touch above the head'. This first item will not contribute to the total score. The remaining 19 items are assessed on a three point scale using the following criteria: 0 - Unable to achieve independently; 1 - Modified method but achieves goal independent of physical assistance from another person; 2 - Normal – achieves goal without any assistance. For each item, a score will be collected on the left and right side. A derived total score will be calculated by summing the scores from these 19 individual items and ranges from 0 if the subject fails all activities to 38 if the subject achieves all activities. If, for an individual item, a response is recorded for both the left and right side the highest score will be used in calculating the total. If 3 or fewer items are still missing responses then it will be assumed that the score was 0. If greater than 3 items are missing, then the total score will be set to be missing.

#### 5.6.4.1 Final analysis

##### *Main analysis*

The main analysis is to compare the change from baseline upper limb module test total score at 15 months between the two treatment groups based on the ITT Set. The method of multiple imputation will be used as described for the HFMSE. The change will be compared between treatment groups by analysis of covariance with treatment group as the factor and subject age at screening and baseline value as covariates.

##### *Sensitivity analysis*

Four sensitivity analyses will be performed. In the first, the analysis described above will be performed on the PPS. In the second, the analysis will be performed using a Mixed Effects Model with Repeated Measures (MMRM) with an unstructured covariance matrix, where the treatment group, time (as a categorical covariate), treatment by time interaction, and patient age at screening will be included in the model as fixed effects; patient will be a random effect; baseline upper limb score and baseline upper limb score by time interaction will be included as a covariate. No imputation for missing visit data will be performed and the analysis will be performed on the ITT Set. In the third, the main analysis will be repeated but for subjects who terminate the study prior to the 15-month assessment due to treatment failure or death, the worst of the last observed value or the baseline value will be imputed. In the fourth sensitivity analysis, only the subset of subjects in the ITT Set who have non-missing values at 15 months will be analyzed. For both of these treatment groups will be compared by analysis of covariance.

#### 5.6.4.2 Summary of analyses

##### **Summary of analyses for the secondary endpoint, Change from baseline in upper limb module test at 15 months**

Analysis Method	Final Analysis - Population: further notes
Main analysis	Analysis of covariance (treatment as fixed effect) with subject's age at screening and baseline value as covariates
Sensitivity analyses	Analysis of covariance (treatment as fixed effect) with subject's age at screening and baseline value as covariates
	MMRM model - treatment group, time (as a categorical covariate), treatment by time interaction, and patient age at screening will be included in the model as fixed effects; patient will be a random effect; baseline upper limb score and baseline upper limb score by time interaction will be included as a covariate.
	ITT, missing data handled using multiple imputation method
	PPS, missing data handled using multiple imputation method
	ITT: no imputation for missing data

Analysis of covariance (treatment as fixed effect) with subject's age at screening and baseline value as covariates	ITT Set with Multiple imputation; worst of the baseline and last observed value for subjects who discontinue due to treatment failure or death. If missing for any other reason then use value from MI
Analysis of covariance (treatment as fixed effect) with subject's age at screening and baseline value as covariates	ITT, with non-missing 15-month values

### 5.6.5 Proportion of subjects who achieve standing alone at 15 months

#### 5.6.5.1 Final analysis

##### *Main analysis*

The main analysis will be performed on the ITT Set and missing data will be imputed as described in Section 5.6.2. If, a subject terminates the study prior to the 15-month assessment due to treatment failure or death then any imputed value will be ignored and the subject will be considered as a non-responder. For the remaining subjects, if the subject was unable to achieve standing alone at baseline but could achieve this at Month 15 then they will be considered a responder. Treatment groups will be compared using logistic regression adjusting for each subject's age at screening and baseline ability to stand alone.

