## 5. SUBJECT ELIGIBILITY

### 5.1 Inclusion Criteria

Subjects must meet all of the following criteria at Screening to be eligible:

1. Signed informed consent of parent or guardian. Signed informed assent of subject, if indicated per subject's age and institutional guidelines
2. Genetic documentation of 5q SMA (homozygous gene deletion, mutation, or compound heterozygote)
3. Onset of clinical signs and symptoms consistent with SMA at > 6 months of age
4. Males and females 2 to 12 years of age
5. Can sit independently, but has never had the ability to walk independently
6. Motor Function Score (Hammersmith Functional Motor Scale – Expanded)  $\geq 10$  and  $\leq 54$  at Screening
7. Able to complete all study procedures, measurements and visits and parent or guardian/subject has adequately supportive psychosocial circumstances, in the opinion of the Investigator
8. Estimated life expectancy > 2 years from screening, in the opinion of the Investigator
9. Meets age-appropriate institutional criteria for use of anesthesia/sedation, if use is planned for study procedures (as assessed by the Site Investigator and either anesthesiologist or pulmonologist)
10. For subjects who, in the opinion of the Investigator, have reached reproductive maturity, satisfy 1 of the following:

Females: have a negative pregnancy test at Screening and agrees to employ adequate contraceptive measures for the duration of the study. Acceptable contraception methods are restricted to abstinence, barrier contraceptives, intrauterine contraceptive devices or licensed hormonal products.

Males: be abstinent for the duration of the study

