#### *Imputation for motor milestones*

If for a milestone either ‘No (refusal)’ or ‘Unable to test’ are observed at a visit then the result will be first set to missing. Imputation will be performed for missing data considering each milestone separately using the following rules for scheduled visits.

For baseline, the closest non-missing milestone prior to or at first dose will be selected. If the motor milestone is still missing then the missing value will be imputed as the median of the non-missing values of the stratum to which the subject belongs to: Age at screening < 6 years or Age at screening  $\geq$  6 years. In the event that the median at baseline is 0.5 then then the missing value will be imputed as 1. If, for the subject with a missing value at a particular visit the corresponding visit is flanked by visits with non-missing milestones, the missing value will be imputed by using the worst result from the flanking visits. Otherwise, if the imputation is the last visit, the missing value will be imputed as the lowest value observed across all subjects who have a non-missing value at this visit within the stratum: Age at screening < 6 years or Age at screening  $\geq$  6 years within the treatment group. Of note, only observed data will be utilized for imputation purposes and in a situation where unscheduled visit data is available these values will be utilized if these flank a missing visit. Missing motor milestone items will be imputed first prior to any analysis.

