##### **5.6.2.1 Final analysis**

###### *Main analysis*

Treatment groups will be compared using logistic regression adjusting for each subject’s age at screening and baseline number of milestones. Missing data will be handled as described in Section 5.6.2. If a subject terminates the study prior to the 15-month assessment due to treatment failure or death then any imputed value will be ignored and the subject will be considered a non-responder. For the remaining subjects, the 15-month milestone data will be

assessed and if the baseline milestones achieved are still maintained at Month 15 and the subject has achieved at least one new milestone, he/she will be considered a responder.

Should the number of responders be less than 5 in either group, Fisher's exact test will be used instead. If Fisher's exact test is used, the unconditional confidence interval for the difference in response rates will be provided (Santner and Snell 1980).

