### 5.6.6 Proportion of subjects who achieve walking with assistance at 15 months

This will be analyzed using the same main and sensitivity methods as described in Section 5.6.5.

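### Standing alone and walking with assistance: children who already have the skill at baseline stay in the denominator as certain non-responders, which dilutes the reported proportions and leaves the baseline-ability term without a finite estimate

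*SAP*

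**What the plan says.** - **Analysis set, SAP 5.6.5.1.** "The main analysis will be performed on the ITT Set and missing data will be imputed as described in Section 5.6.2".
- **Responder rule, same section.** After children who terminate because of treatment failure or death have been set to non-responder, "if the subject was unable to achieve standing alone at baseline but could achieve this at Month 15 then they will be considered a responder". No rule is written for a child who could already stand alone at baseline.
- **Model, same section.** "Treatment groups will be compared using logistic regression adjusting for each subject's age at screening and baseline ability to stand alone".
- **Walking with assistance, SAP 5.6.6.** "This will be analyzed using the same main and sensitivity methods as described in Section 5.6.5".
- **Sensitivity analyses, SAP 5.6.5.** The four analyses change the population or the handling of missing data. None changes the responder rule.
- **Eligibility, Protocol 5.1.** The motor criterion is "Can sit independently, but has never had the ability to walk independently", with an HFMSE score of 10 to 54 at Screening. SAP 5.6.2 expects all children to sit without support and none to walk alone at baseline. It does not mention standing alone or walking with assistance in that expectation.
- **Baseline imputation, SAP 5.6.2.** A baseline milestone that is still missing takes its age-stratum median, and "In the event that the median at baseline is 0.5 then then the missing value will be imputed as 1". Imputation can therefore also place a child in the able group.
- **Sparse data, SAP 5.6.2.1.** "Should the number of responders be less than 5 in either group, Fisher's exact test will be used instead". This is written for the endpoint of any new milestone and is not repeated in 5.6.5 or 5.6.6.
- **Status.** These are the fifth and sixth secondary endpoints in the sequence tested at 0.05 (SAP 5.2). Protocol 10.6.3 bases the primary analysis of each secondary endpoint on the ITT Set.

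**The concern.** The endpoint asks who gains a skill, but the denominator includes children who cannot gain it. The adjustment for "baseline ability to stand alone" serves a purpose only if some children are able at entry, so the plan itself allows for them.

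Three things follow if any are enrolled:

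1. The reported proportion combines the chance of gaining the skill with the share who already had it.
2. That share can differ between arms by chance, most easily in the smaller Efficacy Set that SAP 3 uses for milestones after an early stop. The crude difference then moves for a reason unrelated to treatment.
3. Everyone in the able group has the same outcome by definition, so the baseline-ability term is not estimable. Neither section says what to do, and the choice would be made with the data in view on endpoints under alpha control.

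Within these two endpoints, a child who keeps the skill and a child who loses it also receive the same score.

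**Working it through.** **Inputs.** The arm sizes of 84 and 42 come from the re-randomisation step in SAP 5.1. The share able at baseline, *b*, and the acquisition rates are not in the documents. Every value of them below is an assumption. The plan states no rate or power for these two endpoints, so there is no figure of its own to reproduce.

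**Step 1: dilution.** With at-risk acquisition rate *a*, the reported proportion is *a* × (1 − *b*). If *b* is equal in the arms, the difference shrinks by the same factor. Assume *a* = 20% v 5%:

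| *b* | Reported | Difference (points) | Crude odds ratio |
|---|---|---|---|
| 0 | 20.0% v 5.0% | 15.0 | 4.75 |
| 5% | 19.0% v 4.75% | 14.25 | 4.70 |
| 10% | 18.0% v 4.5% | 13.5 | 4.66 |
| 20% | 16.0% v 4.0% | 12.0 | 4.57 |
| 30% | 14.0% v 3.5% | 10.5 | 4.49 |

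The proportions and the difference move. The crude odds ratio hardly does.

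**Step 2: imbalance.** Let acquisition be 20% in both arms, with *b* = 15% v 5%. The reported values are 0.20 × 0.85 = 17% and 0.20 × 0.95 = 19%, a two-point gap with no treatment effect.

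**Step 3: the stated model.** Illustration: 8 of 84 and 4 of 42 are able at baseline, and 14 v 3 gain the skill. The able group has 0 responders of 12 and the rest 17 of 114, which is quasi-complete separation. Logistic regression on treatment, age and baseline ability, stopped at successive iterations, gives:

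| Iterations | Baseline-ability coefficient (SE) | Treatment log odds ratio (SE) |
|---|---|---|
| 5 | −4.8 (4.6) | 0.9212 (0.674) |
| 10 | −9.8 (56) | 0.9212 (0.675) |
| 20 | −19.8 (8,274) | 0.9212 (0.675) |
| 25 | −24.8 (about 100,000) | 0.9212 (0.675) |

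Fitting treatment and age only in the 114 children unable at baseline gives 0.9212 (SE 0.675). The likelihood-ratio chi-square for treatment is 2.140 in both fits.

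A second case can be checked by hand. Keep 8/84 and 4/42 able, let 10 v 3 gain the skill, and leave age out. Among children unable at baseline the table is 10/76 v 3/38, so

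- log odds ratio = ln[(10/66)/(3/35)] = 0.570
- SE = √(1/10 + 1/66 + 1/3 + 1/35) = 0.691

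The full ITT model with the baseline-ability term converges to the same two values.

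**Step 4: an unadjusted test.** Two-sided Fisher p-values on the ITT Set and on children unable at baseline:

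| Able at baseline | Gaining | ITT | Unable at baseline |
|---|---|---|---|
| 8/84 v 4/42 | 10 v 3 | 0.541 | 0.539 |
| 8/84 v 4/42 | 14 v 3 | 0.174 | 0.170 |
| 12/84 v 3/42 | 8 v 1 | 0.270 | 0.156 |
| 12/84 v 3/42 | 14 v 2 | 0.087 | 0.049 |

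With an equal able share the effect is negligible. With 14% v 7% able it can cross 0.05.

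**The case against.** **The model can be fitted where it matters.** A reader might infer from the separation that the stated comparison fails. It does not. Only the nuisance coefficient diverges. Step 3 shows the treatment estimate settling on the value from children unable at baseline, because able children contribute nothing to it. A reader might also infer that the tested effect is understated, or that chance imbalance biases it. For the adjusted odds ratio and its test, neither is so. This part of the objection stands in full.

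**Loss of skills is measured elsewhere.** The second-ranked endpoint requires baseline milestones to be maintained (SAP 5.6.2.1), and the third scores a lost milestone −1 (SAP 5.6.3.1). The two endpoints here concern acquisition by name, so it would be wrong to say that the plan ignores loss. What remains is narrower: no table is specified for retention of these two particular skills.

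**The full-ITT proportion is legitimate and follows the protocol.** It answers how many of all treated children newly gained the skill, and Protocol 10.6.3 asks for the ITT Set. That is fair, and it is why the full-ITT figure should still be shown. It does not match the effect that the model estimates, however, and the plan does not point this out.

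**Nothing shows that able children were enrolled.** Correct. The criteria and the covariate permit and anticipate them; they do not count them.

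**Fisher's test may already apply.** SAP 5.3 says that the milestone analyses are detailed in 5.6.2, so the rule for fewer than 5 responders arguably extends to these endpoints. If so, the test would run unadjusted on the diluted ITT table, which strengthens the case for restricting the set.

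**Conclusion.** The point holds for the reported proportions, for their crude difference, and for an unspecified remedy when the baseline term separates. It does not hold for the adjusted treatment comparison, which already equals the comparison among children unable at baseline.

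The size depends on the unknown share able at baseline: assumed shares of 5% to 20% lower the proportions by 5% to 20% in relative terms. If the share is zero, the covariate is constant and nothing is diluted. The formal test is exposed only if the covariate is dropped while the full ITT Set is kept, or if Fisher's test is used on that set. The exposure is usually modest and larger when the arms differ in baseline ability.

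Too few sham responders to estimate the treatment coefficient would be a separate problem, which this change does not solve.

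**What to change.** For SAP 5.6.5 and 5.6.6:

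1. Base the responder proportions and the treatment comparison on ITT children without that milestone at baseline. Apply the same restriction within the Efficacy Set if the study stops early.
2. Remove baseline ability from the model and keep age at screening.
3. Record this as a refinement of the ITT statement in Protocol 10.6.3, and show the full-ITT proportion alongside.
4. Tabulate by arm, among children with the milestone at baseline, how many retain it at Month 15.

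The cost is SAP wording, a note reconciling it with the protocol, one small table, and a slightly smaller denominator. Precision of the adjusted comparison is not lost: in Step 3 the estimate, standard error and likelihood-ratio statistic are the same with and without the able children.

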### 5.3 Multiple Imputation of missing data

In the protocol it was stated that the multiple imputation procedure would be used to impute missing values for all primary and secondary efficacy endpoints. However in finalizing this statistical analysis plan it was decided that to handle the missing data in the WHO motor milestones, the multiple imputation procedure won't be used because historical data showed that it's very rare for non-ambulatory SMA patients to achieve certain milestones (such as walking alone). Therefore, an imputation approach based upon multiple imputation would face challenges due to low or zero numbers of subjects in the sham arm achieving a response. The imputation rules and analyses for motor milestones are detailed in Section 5.6.2.

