### 5.6.5.2 Summary of analyses

#### Summary of analyses for the secondary endpoint, Proportion of subjects who achieve standing alone at 15 months

Analysis Method	Final Analysis - Population: further notes
Main analysis	
Logistic regression adjusting for each subject's age at screening and baseline ability to stand alone. Subjects who terminate the study prior to the 15-month assessment due to treatment failure or death will be considered as a non-responders	ITT, impute missing 15-month values per Section 5.6.2
Sensitivity analyses	
Logistic regression adjusting for each subject's age at screening and baseline ability to stand alone. Subjects who terminate the study prior to the 15-month assessment due to treatment failure or death will be considered as a non-responders	PPS, impute missing 15-month values per Section 5.6.2
Logistic regression adjusting for each subject's age at screening and baseline ability to stand alone. Subjects who terminate the study prior to the 15-month assessment due to treatment failure or death will be considered as a non-responders	ITT
Logistic regression adjusting for each subject's age at screening and baseline ability to stand alone. Subjects who terminate the study prior to the 15-month assessment due to treatment failure or death will be considered as a non-responders	ITT: completed/ discontinued subjects with missing Month 15 not deemed due to treatment failure or death are excluded
Logistic regression adjusting for each subject's age at screening and baseline ability to stand alone	ITT, with non-missing 15-month values

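### Standing alone and walking with assistance (ranks 5 and 6) have no stated sparse-count fallback, so with no sham responders a Wald test of the written logistic model cannot reject, however good the drug result

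*SAP*

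**What the plan says.** SAP 5.2 ranks standing alone fifth and walking with assistance sixth among the secondary endpoints, tested in sequence at alpha 0.05. Protocol 10.6.3 makes tests two-sided.

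- **Standing alone (SAP 5.6.5.1).** "Treatment groups will be compared using logistic regression adjusting for each" subject's "age at screening and baseline ability to stand alone". The section cites 5.6.2 for one purpose only: "missing data will be imputed as described in Section 5.6.2". The summary table (5.6.5.2) does the same: "impute missing 15-month values per Section 5.6.2". No test statistic is named and nothing is said about few events.
- **Walking with assistance (SAP 5.6.6).** "This will be analyzed using the same main and sensitivity methods as described in Section 5.6.5".
- **Any new milestone (SAP 5.6.2.1).** "Should the number of responders be less than 5 in either group", the logistic model gives way to Fisher's exact test, with an unconditional confidence interval for the difference in response rates.
- **Milestones in general (SAP 5.3).** Multiple imputation was dropped because the sponsor foresaw "low or zero numbers of subjects in the sham arm achieving a response" on certain milestones; the example given is walking alone. The same paragraph adds: "The imputation rules and analyses for motor milestones are detailed in Section 5.6.2".

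**The concern.** Each of these endpoints is a single milestone, so each will generally have fewer responders than the any-new-milestone endpoint. The SAP foresaw sparse counts and wrote a fallback for that broader endpoint, but not for the two narrower ones.

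Followed literally with no sham responders, 5.6.5.1 gives an infinite odds ratio. The p-value then depends on which statistic is read from the output, and a Wald p-value is uninformative.

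At stake is the verdict on an alpha-controlled endpoint. Failure at rank 5 also makes rank 6 exploratory. If the test were chosen after unblinding, the data could drive that choice.

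**Working it through.** **Inputs.** Arms of 84 and 42 (SAP 5.1, resampling step); two-sided 0.05 (Protocol 10.6.3, SAP 5.2); fallback threshold of fewer than 5 responders in either arm (SAP 5.6.2.1). The documents give no response rate for either endpoint, so all rates below are assumptions. They give no power figure for these endpoints either; the only one, at least 90%, is for the primary endpoint and does not bear on this point. P-values are unadjusted.

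**Step 1: why Wald fails at zero.** With a drug responders and b sham responders,

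log OR = ln[a(42 − b) / (b(84 − a))], SE = √(1/a + 1/(84 − a) + 1/b + 1/(42 − b)).

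At b = 0 both are infinite for every a > 0. In iterative fitting at 8/84 versus 0/42 the Wald p-value drifts towards 1 (0.61 after 9 iterations, 0.997 after 21). Adjusting for age does not remove this separation.

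**Step 2: Fisher on the same data.** At 9/84 versus 0/42 the drug-favouring tail is (84·83·…·76)/(126·125·…·118) = 0.0224. The opposite tail adds 0.0063, giving p = 0.029. At 8/84 versus 0/42, p = 0.051. The likelihood-ratio (LR) p-values are 0.006 and 0.009.

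**Step 3: one sham responder.** At 13/84 versus 1/42, log OR = ln(13·41/71) = 2.016 and SE = √(1/13 + 1/71 + 1 + 1/41) = 1.056, so z = 1.91 and Wald p = 0.056. Fisher gives 0.034 and LR 0.014.

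**Step 4: fewest drug responders of 84 for p < 0.05 (tables favouring drug).**

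| Sham responders of 42 | LR | Fisher | Wald |
|---|---|---|---|
| 0 | 5 | 9 | never |
| 1 | 10 | 13 | 14 |
| 2 | 14 | 16 | 16 |
| 3 | 17 | 18 | 19 |
| 4 | 20 | 22 | 21 |

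The tests can also differ in tables favouring sham: 0/84 versus 2/42 gives LR 0.035 and Fisher 0.109. Step 5 includes such tables.

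**Step 5: how often the rule changes the verdict.** Sum the binomial probabilities over all 85 × 43 tables. The rule uses Fisher if either arm has fewer than 5 responders, and otherwise the named logistic statistic.

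| Assumed rate, drug vs sham | Rule vs plain Wald | Rule vs plain LR |
|---|---|---|
| 2% vs 0% | 0.0% | 2.7% |
| 5% vs 1% | 1.6% | 26% |
| 10% vs 1% | 32% | 38% |
| 15% vs 1% | 62% | 17% |
| 10% vs 5% | 6% | 13% |
| 20% vs 5% | 16% | 11% |
| 30% vs 10% | 3% | 2.5% |

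Against Wald, the rule mostly turns a non-significant result into a significant one. Against LR, it removes significance. The chance of 0 of 42 sham responders is 0.99^42 = 66% at an assumed sham rate of 1% and 0.95^42 = 12% at 5%. The chance of fewer than 5 is above 99.9% and 94%, so the rule, if it applies, would nearly always be triggered at these rates.

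**Step 6: size under equal rates.** At common rates of 1%, 2%, 5% and 10%, Fisher's true size is 0.4%, 1.3%, 2.6% and 3.2%; LR's is 3.0%, 5.3%, 8.0% and 5.9%. LR is therefore not a safe default here.

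**Step 7: the baseline covariate.** Under 5.6.5.1 a responder must have been unable to stand alone at baseline. A child who could stand alone at baseline is therefore always a non-responder. If any such child is enrolled, the covariate is separated; if none is, it is constant. Either way its coefficient cannot be estimated. The same holds for walking with assistance if 5.6.6 is read, as seems intended, with baseline ability for that milestone as the covariate.

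**The case against.** The best counter-argument is SAP 5.3: "The imputation rules and analyses for motor milestones are detailed in Section 5.6.2". These two endpoints are motor milestones and the Fisher rule sits within 5.6.2, so the rule may already cover them. That is a fair reading but not a clear one. Section 5.6.5.1 sets its own covariate and its own responder definition, so 5.6.2.1 does not simply govern it, and both 5.6.5.1 and its table cite 5.6.2 for imputation alone. A reader might equally infer that the SAP rules the fallback out; no sentence says that either.

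A second objection is that leaving the logistic statistic unnamed is routine. This stands. The omission runs through the SAP and also touches ranks 1 and 2 (5.6.1.1, 5.6.2.1). Only the missing fallback is particular to ranks 5 and 6.

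Third, the larger percentages rest on sham rates of 0% to 1%, which the SAP does not predict for these endpoints; its only example is walking alone. This also stands, and is why the table includes sham rates of 5% and 10%.

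Fourth, rank 5 is formally tested only if the primary and four earlier secondaries succeed. The probabilities are not conditioned on that, and without age adjustment the single-patient thresholds are illustrative.

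**Conclusion.** The gap is real and minor. For two alpha-controlled endpoints the written model has no stated fallback. In the zero-sham case, which the SAP foresees for some milestones, a Wald test cannot reject while the SAP's own Fisher rule rejects from 9/84.

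The chance that applying the rule changes the verdict runs from 0.0% to 62% against Wald and from 2.5% to 38% against LR over the assumed rates. It is small when drug response is very rare and Wald is used, or when both arms respond often. An early final analysis would use a smaller milestone set (SAP 3 and 5.6.7), making sparse counts more likely.

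A reader might infer that the verdict is unstable in most trials. Comparing Wald, LR, Firth and Fisher together, the chance that not all four agree is 27%, 69% and 79% at 5%, 10% and 15% versus 1%. The documents do not support using those figures as the size of the problem: the SAP never mentions Firth, and all three assume a 1% sham rate. The question the SAP raises is whether its own rule applies. The primary endpoint and ranks 1 to 4 are not affected by the missing fallback.

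**What to change.** State in SAP 5.6.5 and 5.6.6, before unblinding, that the 5.6.2.1 rule applies: Fisher's exact test, with the unconditional confidence interval, when either arm has fewer than 5 responders. Drop the baseline-ability covariate from these two logistic models and keep screening age and the ITT Set. As a separate SAP-wide clarification, name the statistic that supplies logistic p-values above the threshold.

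This takes two or three sentences. The statistical cost is that Fisher's test is unadjusted and conservative (true size 0.4% to 3.2% at common rates of 1% to 10%), so a result such as 8/84 versus 0/42 would narrowly miss at p = 0.051.
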